The effect of formulation may have implications for dosage and administration recommendations. This study will evaluate the relative bioavailability of the LY3337641 test formulation, commercial image tablet (esylate salt) [T1_{fasted}] compared to the reference formulation, Phase 1/2 tablet (diHCl salt) [R_{fasted}]. In addition, this study will evaluate the relative bioavailability of the large active pharmaceutical ingredient (API) particle size distribution (PSD) commercial image tablet (esylate salt) [T2_{fasted}] compared to the test formulation, commercial image tablet (esylate salt) [T1_{fasted}]. This study will also evaluate the effect of a high-fat meal on the relative bioavailability of the LY3337641 commercial image tablet (esylate salt) [T1_{fed}].

Objectives/Endpoints:

Objectives	Endpoints

Primary
 
To evaluate the relative bioavailability of a single 20-mg dose of LY3337641 as the commercial image tablet (esylate salt) [T1_{fasted}] compared to the Phase 1/2 tablet (diHCl salt) [R_{fasted}].
	
Ratio of least square means between T1_{fasted} and R_{fasted} for C_{max} and AUC(0-∞).

Secondary
 
 To evaluate the effect of a high-fat meal on the bioavailability of a single 20-mg dose of LY3337641 when administered as the commercial image tablet (esylate salt) [T1_{fed}]. To evaluate the relative bioavailability of a single 20-mg dose of LY3337641 when administered as the large API PSD commercial image tablet (esylate salt) [T2_{fasted}] compared to the commercial image tablet (esylate salt) [T1_{fasted}]. To assess the tolerability of LY3337641 when administered as a single 20-mg dose to healthy subjects. 	
Ratio of least square means between T1_{fed} and T1_{fasted} for C_{max} and AUC(0-∞).
 
Ratio of least square means between T2_{fasted} and T1_{fasted} for C_{max} and AUC(0-∞).
 
Incidence of treatment-emergent adverse events (TEAEs).

Summary of Study Design:

This is an open-label, 4-period, 4-sequence, randomized, crossover study in healthy subjects.

Subjects will be admitted to the clinical research unit (CRU) on Day -1 of Period 1. In each treatment period, subjects will be fasted overnight for at least 10 hours and a single dose of their assigned treatment will be administered on the morning of Day 1, following a high-fat meal if applicable. At a minimum, subjects will reside at the CRU until the collection of the 72-hour pharmacokinetic blood sample; all subsequent assessments may be conducted on an outpatient visit at the discretion of the investigator.

Blood samples will be collected up to 72 hours (3 days) after each dosing occasion for the measurement of plasma concentrations of LY3337641.

Safety assessments performed during the study will include recording of adverse events (AEs), clinical laboratory evaluations, vital signs, 12-lead electrocardiograms (ECGs), and physical examinations.

Treatment Arms and Duration:

Subjects will receive single oral doses of 20 mg LY3337641 on 4 separate occasions, as the Phase 1/2 tablet (diHCl salt) in the fasted state (R_{fasted}), as the commercial image tablet (esylate salt) in the fasted state ($T1_{\text{fasted}}$) and following a high-fat meal ($T1_{\text{fed}}$), and as the large API PSD commercial image tablet (esylate salt) in the fasted state ($T2_{\text{fasted}}$). There will be a washout period of at least 5 days between dose administrations in consecutive periods.

Number of Subjects:

Up to 32 subjects may be enrolled in order to ensure that at least 24 subjects complete the study.

Statistical Analysis:

Pharmacokinetic parameter estimates for LY3337641 will be compared between formulations and between the fed and fasted states. Log-transformed C_{max} and area under the concentration versus time curve estimates will be evaluated in a linear mixed-effects model with fixed effects for treatment, period, and sequence, and random effect for subject. The treatment differences will be back-transformed to present the ratios of geometric means and the corresponding 90% confidence interval (CI).

The t_{max} will be analyzed non-parametrically. Median of differences and approximate 90% CI for the median of differences will be calculated for the fed versus fasted states and for the comparisons between the different formulations.

2. Schedule of Activities

Study Schedule Protocol I8K-MC-JPDF

	Screening	Periods 1, 2, 3, and 4			Follow-up/ Early discontinuation	Comments
Procedure	Up to 28 days prior to enrollment	Day -1	Days 1 to 3	Day 4	≥7 days after last dose	
Informed Consent	X					
Subject Admission to CRU		X				
Subject Discharge from CRU				X		
Outpatient Visit					X	
Study Drug Administration			Day 1, 0 h			
Medical History	X					
Height	X					
Weight	X				X	
Vital Signs (Supine)	X		Predose, 1, 2, 4, 8, 24, 48 h	72 h	X	Supine blood pressure and/or pulse rate may be measured as clinically indicated. Additional vital signs may be measured during each study period, if warranted and agreed by the investigator.
Clinical Lab Tests	X		Predose, 24 h	X	X	See Appendix 2 , Clinical Laboratory Tests, for details.
Pregnancy Test	X	X			X	Serum pregnancy test will be performed at screening. Urine pregnancy test will be performed at other times.
Physical Exam/Medical Assessment	X		Predose	X	X	After screening, medical assessment only performed to include medical review and targeted examination, as appropriate.
Single 12-lead ECG	X		Predose, 1, 2, 24 h	72 h	X	

PK Samples			Predose, 0.25, 0.5, 0.75, 1, 1.5, 2, 3, 4, 5, 6, 9, 12, 24, 36, 48 h	72 h		Sampling times are relative to the time of study treatment administration (0 min). These are scheduled sampling times; the actual date and time of each PK sample will be recorded. Minor time deviations (e.g. ± 5 min for samples prior to 24 hours) will not be considered a protocol violation.
Genetic Sample			Predose (Period 1 only)			Single sample for pharmacogenetic analysis taken on Day 1 of Period 1.

Abbreviations: CRU = clinical research unit; ECG = electrocardiogram; ED = early discontinuation; h = hour(s); PK = pharmacokinetics.

Note: Predose assessments/sampling will be performed within 4 hours of dosing.

3. Introduction

3.1. Study Rationale

The effect of formulation may have implications for dosage and administration recommendations. The aim of this study is to evaluate the relative bioavailability of the LY3337641 test formulation, commercial image tablet (esylate salt) [T1_{fasted}] compared to the reference formulation, Phase 1/2 tablet (diHCl salt) [R_{fasted}]. In addition, this study will evaluate the relative bioavailability of the large active pharmaceutical ingredient (API) particle size distribution (PSD) commercial image tablet (esylate salt) [T2_{fasted}] compared to the test formulation, commercial image tablet (esylate salt) [T1_{fasted}]. This study will also evaluate the effect of a high-fat meal on the relative bioavailability of the LY3337641 commercial image tablet (esylate salt) [T1_{fed}].

A tablet formulation using the diHCl salt has been utilized in Phase 1 and Phase 2a studies. Two tablet strengths, 5 and 20 mg, were developed. Since the diHCl salt has a tendency to disproportionate (physical instability liability), an alternative salt (esylate) has been pursued for commercial development. The esylate salt is more physically stable and has comparable solubility to the diHCl. Neither the diHCl nor the esylate salt is considered highly soluble per Biopharmaceutics Classification System (BCS) guidance. Hence, understanding the impact of drug substance particle size on in vivo performance is needed to determine what particle size range can be used to supply clinical trials and to justify specifications upon common technical document submission. A 20 mg tablet strength of the esylate salt is the highest tablet strength developed so far and is the strength to be used in this relative bioavailability study.

A pilot food effect evaluation using the Phase 1/2 tablet (diHCl salt) showed that administration of LY3337641 after a high-fat meal did not affect the extent of oral absorption (area under the concentration versus time curve [AUC]) but decreased the rate of absorption, resulting in a 13% lower maximum observed drug concentration (C_{max}) and delayed time to the maximum observed drug concentration (t_{max}) by 1.5 hours. Based on these findings, a high-fat meal is not expected to have a significant effect on the bioavailability of LY3337641 when administered as the commercial image tablet (esylate salt) formulation.

3.2. Background

LY3337641 is an orally available, irreversible inhibitor of Bruton's tyrosine kinase (BTK), a member of the TEC family of cytoplasmic tyrosine kinases. Bruton's tyrosine kinase is a key signaling molecule in the B-cell-receptor and Fc-receptor pathways and an essential mediator of B-cell- and myeloid-cell-dependent inflammatory arthritis (Di Paolo et al. 2011; Chakravarty et al. 2013). Bruton's tyrosine kinase is primarily expressed in hematopoietic cells, including B-cells, mast cells, and macrophages. In humans, BTK loss-of-function mutations cause nonlethal X-linked agammaglobulinemia, resulting in reduced B-cell and immunoglobulin (Ig) levels (Smith et al. 1994).

LY3337641 demonstrates potent, irreversible BTK inhibition in BTK enzyme assays, cell-based BTK phosphorylation assays, and BTK occupancy assays.

Preclinical data suggests that LY3337641 may be useful for treatment of a variety of autoimmune diseases.

In healthy adult subjects, LY3337641 was rapidly absorbed after oral administration in the fasted state, with geometric mean t_{max} ranging from 1 to 3 hours after a single dose and 1 to 2 hours after multiple doses, and elimination of LY3337641 from systemic circulation was rapid; the geometric mean half-life associated with the terminal rate ($t_{1/2}$) was 4.6 to 6.6 hours.

The metabolism of LY3337641 has not been fully elucidated. However, two metabolites, N-demethylation (M1) and N-oxidation (M2), have been detected in human plasma and urine. M1 and M2 plasma concentrations are low relative to parent concentrations in humans. Mean renal excretion of unchanged LY3337641 was <0.5% of the administered dose in humans. In excretion studies in rats and monkeys in which radiolabelled [^{14}C] LY3337641 was orally administered, the urine recovery of total radioactivity (metabolites and/or parent compound) was $\leq 3\%$ of the administered dose, so renal elimination is expected to be a minor clearance route in humans.

3.3. Benefit/Risk Assessment

A single Phase 1 study (Study I8K-MC-JPDD [JPDD]) was conducted in healthy adult males to determine the safety, tolerability, pharmacokinetics (PK), and food effect of single and multiple doses of orally administered LY3337641. In the single dose portion of the study, the drug was well tolerated following single doses ranging from 10 to 200 mg. In the 20 mg dosing arm, 4 of the 6 subjects administered LY3337641 reported 6 treatment-emergent AEs (TEAEs), only one of which (nausea, mild intensity) was attributed to study drug. In the multiple-dosing portion of the study (14 days duration, once daily and twice-daily dosing), the drug was generally well tolerated at dosages up to 40 mg once daily. At dosages totaling 80 mg per day and higher, significant TEAEs (ie, TEAEs leading to discontinuation or deemed clinically significant by the investigator) were reported. The majority of these events involved skin-related manifestations, the most common being rash, with an onset occurring on or after 10 days of LY3337641 administration. Some cases were associated with systemic signs and symptoms, such as fever, arthritis, and laboratory abnormalities. Skin related TEAEs were all accompanied with a rise in C-reactive protein and in one subject with a mild increase in tryptase as well. In Study JPDD, over a dose range of 10 to 200 mg single oral doses, C_{max} and AUC of LY3337641 were proportional to dose.

On the basis of projected BTK occupancy using the Phase 1 data, 20 mg is expected to be in the clinically efficacious dose range. The Phase 1 safety profile supports further clinical development of LY3337641 for treatment of autoimmune diseases; LY3337641 is currently progressing into Phase 2 at dose levels of 5, 10, and 30 mg once daily.

More information about the known and expected benefits, risks, serious adverse events (SAEs) and reasonably anticipated adverse events (AEs) of LY3337641 are to be found in the Investigator's Brochure (IB).

4. Objectives and Endpoints

Table JPDF.1 shows the objectives and endpoints of the study.

Table JPDF.1. Objectives and Endpoints

Objectives	Endpoints

Primary
 
To evaluate the relative bioavailability of a single 20-mg dose of LY3337641 as the commercial image tablet (esylate salt) [$T1_{\text{fasted}}$] compared to the Phase 1/2 tablet (diHCl salt) [R_{fasted}].
	
Ratio of least square means between $T1_{\text{fasted}}$ and R_{fasted} for C_{max} and $AUC(0-\infty)$.


Secondary
 
 • To evaluate the effect of a high-fat meal on the bioavailability of a single 20-mg dose of LY3337641 when administered as the commercial image tablet (esylate salt) [$T1_{\text{fed}}$]. • To evaluate the relative bioavailability of a single 20-mg dose of LY3337641 when administered as the large API PSD commercial image tablet (esylate salt) [$T2_{\text{fasted}}$] compared to the commercial image tablet (esylate salt) [$T1_{\text{fasted}}$]. • To assess the tolerability of LY3337641 when administered as a single 20-mg dose to healthy subjects. 	
Ratio of least square means between $T1_{\text{fed}}$ and $T1_{\text{fasted}}$ for C_{max} and $AUC(0-\infty)$.
 
Ratio of least square means between $T2_{\text{fasted}}$ and $T1_{\text{fasted}}$ for C_{max} and $AUC(0-\infty)$.
 
Incidence of treatment-emergent adverse events (TEAEs).

5. Study Design

5.1. Overall Design

This is an open-label, 4-period, 4-sequence, randomized, crossover study in healthy subjects. Up to 32 subjects may be enrolled in order to ensure that at least 24 subjects complete the study (ie, complete all 4 treatment periods).

Subjects will receive single oral doses of 20 mg LY3337641 on 4 separate occasions. Each subject will receive the following:

- Reference formulation (R_{fasted}): 20 mg LY3337641 Phase 1/2 tablet (diHCl salt) administered in the fasted state;
- Test formulation 1 ($T1_{\text{fasted}}$): 20 mg LY3337641 commercial image tablet (esylate salt) administered in the fasted state;
- Test formulation 1 ($T1_{\text{fed}}$): 20 mg LY3337641 commercial image tablet (esylate salt) administered in the fed state;
- Test formulation 2 ($T2_{\text{fasted}}$): 20 mg LY3337641 large API PSD commercial image tablet (esylate salt) administered in the fasted state.

Subjects will be randomly allocated to one of the treatment sequences below ([Table JPDF.2](#)).

Table JPDF.2. Treatment Sequences in Study I8K-MC-JPDF

Sequence	Period 1	Period 2	Period 3	Period 4
1	Reference formulation (R_{fasted})	Test formulation 2 ($T2_{\text{fasted}}$)	Test formulation 1 ($T1_{\text{fasted}}$)	Test formulation 1 ($T1_{\text{fed}}$)
2	Test formulation 1 ($T1_{\text{fasted}}$)	Reference formulation (R_{fasted})	Test formulation 1 ($T1_{\text{fed}}$)	Test formulation 2 ($T2_{\text{fasted}}$)
3	Test formulation 1 ($T1_{\text{fed}}$)	Test formulation 1 ($T1_{\text{fasted}}$)	Test formulation 2 ($T2_{\text{fasted}}$)	Reference formulation (R_{fasted})
4	Test formulation 2 ($T2_{\text{fasted}}$)	Test formulation 1 ($T1_{\text{fed}}$)	Reference formulation (R_{fasted})	Test formulation 1 ($T1_{\text{fasted}}$)

In each period, subjects will be admitted to the clinical research unit (CRU) on Day -1. In each treatment period, subjects will be fasted overnight and a single dose of 20 mg LY3337641 will be administered in the morning of Day 1. Subjects will receive a high-fat meal prior to dosing with LY3337641 if applicable (see Section 6.3.1). Subjects will reside at the CRU until the collection of the 72-hour pharmacokinetic blood sample.

There will be a washout period of at least 5 days between dose administrations in consecutive periods.

If the investigator decides not to administer the first dose to a subject or not to enroll a subject on a particular day, the subject may be rescheduled to participate in the study; and any procedures performed up to that point may be repeated.

Blood samples will be collected up to 72 hours after each dosing occasion for the measurement of plasma concentrations of LY3337641.

Safety assessments will be performed during the study included recording of AEs, clinical laboratory evaluations, vital signs, 12-lead electrocardiograms (ECGs), and physical examinations.

5.2. Number of Participants

Up to 32 subjects may be enrolled in order to ensure that at least 24 subjects complete all 4 periods of the study.

5.3. End of Study Definition

End of the study is the date of the last visit or last scheduled procedure shown in the Schedule of Activities (Section 2) for the last subject.

5.4. Scientific Rationale for Study Design

This will be an open-label study. Blinding is not necessary because the primary endpoint is PK, and thus not vulnerable to subject or investigator bias.

A crossover design is chosen to enable each subject to act as their own control in the assessment of formulation and food effects. Treatment order randomization will prevent any selection bias that might otherwise result from treatment order, and will mitigate period effects.

Conducting the study in healthy subjects mitigates the potential confounding effects of the disease state and concomitant medications in patients.

5.5. Justification for Dose

The dose level of 20 mg is in the expected therapeutic dose range and is high enough to fully characterize the single-dose PK of the compound. This is also the highest unit dose strength. In addition, as single doses up to 200 mg LY3337641 have been well tolerated, the 20-mg dose is considered appropriate for this study.

6. Study Population

Eligibility of subjects for study enrollment will be based on the results of screening medical history, physical examination, vital signs, clinical laboratory tests and electrocardiogram (ECG).

The nature of any conditions present at the time of the physical examination and any preexisting conditions will be documented.

Screening may occur up to 28 days prior to enrollment. Subjects who are not enrolled within 28 days of screening may be subjected to an additional medical assessment and/or clinical measurements to confirm their eligibility.

Prospective approval of protocol deviations to recruitment and enrollment criteria, also known as protocol waivers or exemptions, are not permitted.

6.1. Inclusion Criteria

Subjects are eligible for inclusion in the study only if they meet all of the following criteria at screening and/or enrollment:

- [1] are overtly healthy males or females, as determined by medical history and physical examination
 - [1a] male subjects:
 - agree to use an effective method of contraception and not donate sperm for the duration of the study and for 90 days following the last dose of study drug (see Section 6.3.4)
 - [1b] female subjects:
 - (i) women not of child-bearing potential may participate, and include those who are:
 - a) infertile due to surgical sterilization (hysterectomy, bilateral oophorectomy, or tubal ligation), congenital anomaly such as mullerian agenesis; or
 - b) postmenopausal – postmenopausal is defined as women with an intact uterus who have not taken hormones or oral contraceptives within 1 year, who have had either cessation of menses for at least 1 year, or 6 to 12 months of spontaneous amenorrhea with follicle-stimulating hormone (FSH) consistent with menopause (FSH >40 IU/L).
 - (ii) women of child-bearing potential may participate, and include those who test negative for pregnancy prior to initiation of treatment based on a urine pregnancy test and agree to use one highly effective method of contraception or a combination of 2 effective methods of contraception during the study and for 28 days following the last dose of study drug (see Section 6.3.4).
- [2] aged 21 to 65 years (inclusive) at the time of screening

- [3] have a body mass index of 18.5 to 32.0 kg/m², inclusive
- [4] have clinical laboratory test results within normal reference range for the population or investigative site, or results with acceptable deviations that are judged to be not clinically significant by the investigator
- [5] have venous access sufficient to allow for blood sampling as per the protocol
- [6] are reliable and willing to make themselves available for the duration of the study and are willing to follow study procedures
- [7] are able and willing to give signed informed consent

6.2. Exclusion Criteria

Subjects will be excluded from study enrollment if they meet any of the following criteria at screening and/or enrollment:

- [8] are investigative site personnel directly affiliated with this study and their immediate families. Immediate family is defined as a spouse, biological or legal guardian, child, or sibling
- [9] are Lilly employees
- [10] are currently enrolled in a clinical trial involving an investigational product or any other type of medical research judged not to be scientifically or medically compatible with this study
- [11] have participated, within the last 30 days, in a clinical trial involving an investigational product. If the previous investigational product has a long half-life, 3 months or 5 half-lives (whichever is longer) should have passed
- [12] have previously completed or withdrawn from this study or any other study investigating LY3337641, and have previously received the investigational product
- [13] have known allergies to LY3337641, related compounds or any components of the formulation, or history of significant atopy
- [14] have an abnormality in the 12-lead ECG that, in the opinion of the investigator, increases the risks associated with participating in the study
- [15] have an abnormal blood pressure as determined by the investigator
- [16] have significant history of or current cardiovascular, dermatological (such as eczema, psoriasis, and acne), respiratory, hepatic, renal, gastrointestinal (cholecystectomy is not acceptable), endocrine, hematological, or neurological disorders capable of significantly altering the absorption, metabolism, or elimination of drugs; of constituting a risk when taking the investigational product; or of interfering with the interpretation of data
- [17] have known or ongoing psychiatric disorders
- [18] regularly use known drugs of abuse

- [19] show evidence of human immunodeficiency virus (HIV) infection and/or positive human HIV antibodies
- [20] show evidence of hepatitis C and/or positive hepatitis C antibody
- [21] show evidence of hepatitis B and/or positive hepatitis B surface antigen
- [22] are women who are lactating
- [23] have used or intend to use over-the-counter or prescription medication, including herbal medications, within 14 days prior to planned dosing
- [24] have donated blood or had blood loss of more than 450 mL within 3 months of screening
- [25] have an average weekly alcohol intake that exceeds 21 units per week (males) and 14 units per week (females), or are unwilling to stop alcohol consumption for 48 hours prior to admission in each study period, and while resident in the CRU (1 unit = 12 oz or 360 mL of beer; 5 oz or 150 mL of wine; 1.5 oz or 45 mL of distilled spirits)
- [26] have had symptomatic herpes zoster infection within 3 months of screening
- [27] medical history, examination finding(s) and/or chest radiograph suggestive of active or latent tuberculosis
- [28] have received live vaccine(s) within 1 month of screening, or intend to during the study
- [29] are immunocompromised
- [30] are currently smoking more than 10 cigarettes per day (or equivalent in tobacco or nicotine products) or are unwilling to abide by smoking restrictions as specified in Section 6.3.2
- [31] in the opinion of the investigator or sponsor, are unsuitable for inclusion in the study

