6.3.4. Contraception

Male subjects

Male subjects or their partners will be required to use an effective method of contraception during the study and for 90 days after the last dose of study drug. Acceptable methods of contraception may include:

- Condom (male condom or female condom) in conjunction with spermicidal gel, foam, cream, film, or suppository.

- Diaphragm or cervical vault cap used in conjunction with spermicidal gel, foam, cream, film, or suppository.
- Male sterilization, with the appropriate post-vasectomy documentation of the absence of sperm in the ejaculate.
- True abstinence (this must be due to subject's lifestyle choice; ie, the subject should not become abstinent just for the purpose of study participation). Withdrawal or calendar methods are not considered acceptable.
- Female partner with placement of an effective hormonal intrauterine device.
- Female partner with established use of oral, injected, or implanted hormonal methods of contraception.

Sexual intercourse with pregnant partners should also be avoided during the course of the study unless condoms are used from the time of the first dose until 28 days after dosing.

Male subjects must agree not to donate sperm for the duration of the study and for 90 days following the last dose of study drug

Female subjects of child-bearing potential

Female subjects of child-bearing potential must agree to use one highly effective method of contraception or a combination of 2 effective methods of contraception during the study and for 28 days following the last dose of study drug.

Highly effective methods of contraception are contraceptive measures with a failure rate of <1% per year, and include:

- Intrauterine device (IUD; eg, Mirena). Steel or copper IUDs are not acceptable.
- Established use of oral, implanted, transdermal, or hormonal method of contraception associated with inhibition of ovulation.
- Male sterilization, with verbal confirmation of surgical success
- Bilateral tubal ligation.

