7.7. Concomitant Therapy

The use of topical medication, provided there is no evidence of chronic dosing with the risk of systemic exposure, and occasional acetaminophen/ibuprofen is acceptable at the discretion of the investigator. Additional drugs are prohibited during the study unless required to treat an AE.

If the need for concomitant medication arises, inclusion or continuation of the subject may be at the discretion of the investigator with consultation with a Lilly clinical pharmacologist or clinical research physician. Any additional medication used during the course of the study must be documented.

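### Do the medication bar in exclusion [23] and Protocol Section 7.7 and the contraception rule in Section 6.3.4 make it impossible to follow both?

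*Protocol*

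**What the plan says.** Criterion [23] in Protocol Section 6.2 excludes subjects who "have used or intend to use over-the-counter or prescription medication, including herbal medications, within 14 days prior to planned dosing". It names no exception. The opening text of Section 6 adds that advance approvals of departures from entry criteria, "also known as protocol waivers or exemptions, are not permitted".

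Section 7.7 governs drugs taken on study: "Additional drugs are prohibited during the study unless required to treat an AE". Certain topical products are allowed, and "occasional acetaminophen/ibuprofen is acceptable at the discretion of the investigator". A second paragraph says: "If the need for concomitant medication arises, inclusion or continuation of the subject may be at the discretion of the investigator", in consultation with a sponsor physician or pharmacologist.

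Section 6.3.4 sets the duty for women who could conceive: each "must agree to use one highly effective method of contraception or a combination of 2 effective methods of contraception during the study". The duty runs on until 28 days past the final dose. Four highly effective methods are listed:

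- hormonal contraception, worded as "Established use of oral, implanted, transdermal, or hormonal method of contraception associated with inhibition of ovulation"
- a device placed in the uterus, worded as "Intrauterine device (IUD; eg, Mirena). Steel or copper IUDs are not acceptable"
- sterilisation of the male partner
- bilateral tubal ligation

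**The concern.** Hormonal contraceptives are commonly prescription drugs, and use that counts as established under Section 6.3.4 must already be under way before dosing. A woman who qualifies by that route therefore appears to trigger [23] by the same fact. Section 7.7 does not list contraceptives among its permitted items, and the ban on waivers seems to close the obvious way out. If so, the protocol would invite women of child-bearing potential in one section and turn many of them away in another.

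Two things would be at stake. Screeners might classify the same volunteer differently. And women enrolled on the permissive reading might be recorded as eligibility deviations, which SAP Section 8 says are weighed when subjects are assigned to analysis populations.

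**Working it through.** No figure in the plan depends on this point, so the check is a comparison of the texts, a count, and a look at how the analysis would respond.

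**1. Do the texts clash?**

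| Section | Period covered | Hormonal contraception |
|---|---|---|
| 6.2 [23] | 14 days before planned dosing | not mentioned; barred on a literal reading |
| 7.7 | during the study | not mentioned; discretion clause available |
| 6.3.4 | study plus 28 days after last dose | listed as acceptable |

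Yes. For a woman already using a listed hormonal method, the sections do not say which governs.

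**2. Is the clash unavoidable?** Count the listed methods.

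- Women of child-bearing potential: 2 of 4 highly effective methods are hormonal or drug-releasing (50%). Section 6.1 classes tubal ligation as making a woman not of child-bearing potential. Setting it aside gives 2 of 4 − 1 = 3 (67%).
- The alternative of two effective methods is also open, although Section 6.3.4 gives women no list of these.
- Male subjects: 2 of 6 methods are hormonal (33%). Both are used by the partner, whom [23] and 7.7 do not govern.
- Women not of child-bearing potential: no contraception duty.

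Section 6.3.4 therefore requires a method, not a hormonal one, and some subjects in every group can satisfy all the sections.

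**3. Is a site forced into a breach?** Section 6.1 requires every inclusion criterion to be met, and Section 6.2 removes anyone who meets an exclusion. A site that reads [23] literally declines a user of oral contraceptives and complies with everything: an acceptable-methods list confers no right to enrol. A site that reads Section 6.3.4 as the specific provision enrols her. The risk is two readings, not a compulsory breach.

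**4. What happens to the estimates?** SAP Section 9.3.2 fits, for subject *i* in period *j*,

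log(PK) = treatment + period + sequence + *s*ᵢ + error.

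- *Literal reading.* Fewer such women enrol. The target is still 24 completers from up to 32 enrolled, and each completer is still her or his own control.
- *Permissive reading.* Suppose a stable contraceptive multiplies a woman's exposure by a factor *k* in every period. Then *s*ᵢ becomes *s*ᵢ + log *k*. Her T1 fasted minus R fasted difference contains log *k* − log *k* = 0 from this source. The same holds for fed against fasted T1 and for T2 against T1.

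The sample-size inputs (intra-subject CV of 15% for AUC and 25% for Cmax, giving stated precision of 8% and 13%) contain no term for contraceptive use, and neither reading alters them.

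**5. What happens to the analysis sets?** Protocol Section 10.3 analyses all randomised subjects who were dosed. SAP Section 8 defines the PK population by dosing and evaluable PK data, and the one specific ground it gives for leaving PK data out is early vomiting. Deviations are considered for severity and impact. Protocol Section 8.1.1 already sets a process for subjects found not to meet entry criteria.

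**The case for a change.** The strongest case for acting is that the contradiction is visible on the page and cheap to remove. The escapes are not clean. The discretion clause in Section 7.7 does not mention [23], and reading it as permission to include sits awkwardly with the bar on waivers. A transdermal contraceptive does not obviously fit the topical allowance. The barrier methods in the male list call for spermicide, which could itself be read as an over-the-counter product. Protocol Section 3.2 says the drug's metabolism is not fully worked out, so whether concomitant hormones are allowed deserves a deliberate statement. Two screeners could reach opposite decisions on the same woman, and a deviation could follow.

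Most of this stands as a comment on drafting. What does not stand is the claimed consequence. The documents give no figures by sex, child-bearing status or contraceptive method, so it cannot be said that [23] removes most eligible women. The route from a recorded deviation to a changed analysis population is possible under SAP Section 8, but nothing in the documents makes contraceptive use a ground for exclusion. Unresolved metabolism would matter to these ratios mainly if a contraceptive affected one formulation or meal state differently from another, and the documents give no reason to expect that.

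**Conclusion.** The concern does not hold as a flaw in the plan. A wording gap exists: [23] and Section 7.7 do not say whether the methods listed in Section 6.3.4 are exempt. The sponsor must reconcile these passages, and which one prevails is the sponsor's decision. The gap affects 2 of 4 listed methods for women of child-bearing potential (2 of 3 without tubal ligation) and none of the methods that male subjects themselves use.

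No change to the design, sample size or analysis follows, because the four-way crossover gives sound within-subject comparisons under either reading. This rests on three assumptions:

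- Established contraceptive use is stable across a woman's four periods.
- Any effect on exposure is similar for the four treatments.
- Most subjects complete. Cancellation is exact for complete subjects; for incomplete ones the mixed model uses some between-subject information, where a constant shift adds to between-subject variation.

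The practical cost is possible inconsistency at screening, which the site can settle by asking the sponsor what the criterion means.
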